**2. Objectives****Primary Objective**

To evaluate the impact of ureterorenoscope diameter on intraoperative surgeon stress during ureterorenoscopy.

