## **6. Outcome Measures**

### **Primary Outcome**

- Occurrence of stress-related procedures (defined as  $\Delta\text{STAI-TX1} > 0$ )

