## **9. Statistical Analysis (SAP)**

Statistical analyses were performed using SPSS (version 20.0; IBM, Armonk, NY).

- Continuous variables: Student's t-test or Mann–Whitney U test
- Categorical variables: Chi-square or Fisher's Exact test
- Significance level:  $p < 0.05$

Sample size was calculated using G\*Power (v3.1). Based on prior SFR data, 65 patients per group were required (power 95%, alpha 0.05). Multivariable logistic regression analysis was performed to identify independent predictors of stress-related procedures.

Variables included:

- Ureteroscope caliber
- Stone size
- Stone location
- Operative time

Adjusted odds ratios (aOR) with 95% confidence intervals were calculated. Model calibration was assessed using the Hosmer–Lemeshow test.

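### Section 9 gives two caliber analyses of the primary outcome and names neither as deciding; the one tied to that outcome adjusts for operative time, which the caliber may itself change

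*Combined protocol and SAP*

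**What the plan says.** Section 2 sets the primary objective: "To evaluate the impact of ureterorenoscope diameter on intraoperative surgeon stress during ureterorenoscopy". Section 6 makes the primary outcome binary, "Occurrence of stress-related procedures", meaning a change in STAI-TX1 above zero.

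Section 9 never pairs that outcome with a named primary test. Two of its provisions reach it:

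- A general rule by variable type: "Categorical variables: Chi-square or Fisher's Exact test". Applied to the primary outcome, this is a crude comparison of the two arms.
- A regression that is explicitly about the outcome: "Multivariable logistic regression analysis was performed to identify independent predictors of stress-related procedures". Its terms are "Ureteroscope caliber", stone size, stone location and "Operative time". The output is stated as: "Adjusted odds ratios (aOR) with 95% confidence intervals were calculated".

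One significance level of 0.05 covers all analyses. Nothing calls either analysis primary or supportive, or says what follows if they differ. Section 6 also lists operative time among the secondary outcomes.

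**The concern.** A two-arm trial with one binary primary outcome should have one number that answers its primary question. Here there are two, and they do not estimate the same quantity.

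The crude test compares the arms as randomised, so it captures everything that caliber does to surgeon stress, including anything it does by lengthening or shortening the procedure. The adjusted odds ratio holds operative time fixed. If caliber changes operative time and operative time changes stress, the adjustment takes that pathway out. If unmeasured case difficulty drives both operative time and stress, the adjusted ratio is not a clean direct effect either.

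A real randomised effect could therefore be reported as caliber not being an independent predictor. Equally, the more favourable result could be quoted. Either report would comply with the plan.

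**Working it through.** **1. The plan's own figure.** Section 9 states 65 per group for 95% power at alpha 0.05, based on stone-free rates that it does not give. The figure can be neither reproduced nor refuted. It fits, for example, 90% against 63.8% (two-sided, no continuity correction):

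n = [1.96·√(2 × 0.769 × 0.231) + 1.645·√(0.90 × 0.10 + 0.638 × 0.362)]² / 0.262² = (1.168 + 0.932)² / 0.0686 ≈ 64.3, rounded up to 65.

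This point uses only the 65 per arm.

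**2. Assumptions.** The documents give no stress rates, covariate effects or operative-time difference, so every effect below is assumed. Stone size is standard normal and location has three levels. Operative time = 0.5 × size + shift × caliber + noise. The log-odds of stress is 0.7 per SD of operative time (1.2 in one null case), with a size effect of 0.3 to 0.6. The crude Pearson chi-square is compared with the Wald test of caliber in the four-variable model.

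**3. No caliber effect (4,000 runs per case).** Crude 0.054 and 0.050; model 0.053 and 0.053; at least one significant 0.073 and 0.079. A separate simulation with other effect sizes (6,000 runs per case) gave 0.067 to 0.073, and a further run gave 0.064. Two independent tests would give 1 − 0.95² = 0.0975. The inflation is smaller because the tests are correlated.

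**4. True caliber effect (2,000 runs each).** The split follows by arithmetic: crude only = (disagreement + crude − model) / 2, and model only = disagreement − crude only.

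| Direct log-OR, time shift (SD) | Crude power | Model power | Disagree | Crude only | Model only |
|---|---|---|---|---|---|
| 0.6, 0.3 | 0.47 | 0.33 | 0.18 | 0.16 | 0.02 |
| 0.8, 0.3 | 0.66 | 0.54 | 0.16 | 0.14 | 0.02 |
| 0.8, 0.5 | 0.77 | 0.52 | 0.25 | 0.25 | 0.00 |
| 1.0, 0 | 0.65 | 0.72 | 0.13 | 0.03 | 0.10 |
| 0.5, 0.6 | 0.58 | 0.25 | 0.34 | 0.335 | 0.005 |

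When caliber shifts operative time, almost all disagreement is in one direction: the randomised comparison is significant and the model is not. With no shift, the model has more power.

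**5. How much is due to operative time.** The same scenarios were rerun with a different intercept and location effect. The crude test was compared with the four-variable model, then with the model without operative time.

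| Scenario | Disagree, four-variable | Disagree, without operative time |
|---|---|---|
| 0.6, 0.3 | 17% | 11% |
| 0.8, 0.3 | 17% | 9% |
| 0.8, 0.5 | 28% | 8% |
| 1.0, 0 | 13% | 10% |
| 0.5, 0.6 | 36% | 10% |

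Having two tests accounts for roughly 8–12%; most of the larger figures come from operative time. The percentages move by a few points with the assumed intercept and covariate strengths.

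**6. Boundary cases, again assumed.** If caliber acts on stress wholly through operative time, the crude test rejects in 22–55% of trials and the model in about 5%. If direct and mediated effects oppose each other, crude rejects in 5% and the model in 24%.

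**7. Candidate deciding tests.** In the (0.8, 0.5) scenario, a model with caliber, stone size and location has power 0.81, against 0.76 for the crude test and 0.52 for the four-variable model. Under the null it holds about 0.05.

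**The case against.** The best reply is that section 9 already gives the two analyses different roles. In a two-arm trial, the natural reading is that chi-square or Fisher compares the arms and the regression is follow-up work on predictors, so the gap is one of labelling. That reading is reasonable but unstated, and the text pulls the other way: the regression is the only analysis that mentions the primary outcome.

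Three parts of the reply stand:

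- A reader might infer that the plan lets the trial succeed if either test is significant. No section states such a rule, and the type I inflation if it were applied is small.
- A reader might infer that a significant odds ratio for stone size, location or operative time counts as a primary finding. Section 2 concerns diameter only, so those terms cannot answer it, and false positives among them are not error on the primary question.
- Most of the larger disagreement comes from one covariate, not from having two tests.

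It is also true that the crude test alone holds its level. Adjustment for stone factors is a gain in power and is not needed for validity.

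**Conclusion.** The concern holds in this form: the deciding analysis of the primary outcome is not named, and the only one tied explicitly to that outcome conditions on a post-randomisation variable. That much rests on the text alone.

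The size rests on assumed effects. With 65 per arm and a true effect, the two tests reach different conclusions in about 13–34% of trials, or about 8–12% without operative time. If caliber does not change operative time, the figure is at the low end. Type I error from quoting either test is about 0.06–0.08, so this is not mainly a multiplicity problem. Nor do the documents show that a result was selected; they contain no results. They show only that the plan would not prevent it.

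**What to change.** In section 9, name one deciding test of the randomised caliber contrast on the primary outcome, two-sided at alpha 0.05, without operative time. The preferred choice is a logistic model with caliber, stone size and stone location, reported as a conditional odds ratio. It has somewhat more power than the crude test and needs no new data, because section 8 already collects both stone variables. The unadjusted chi-square or Fisher test would also be valid.

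Label whichever of these two is not chosen as sensitivity, and the four-variable predictor model as exploratory.

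Section 3 reports enrolment from March to December 2025, and section 9 is in the past tense. New wording cannot by itself restore prespecification, so the sponsor should state when the choice was made relative to seeing the results and report both caliber results with their labels.

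The cost is a few sentences. The sponsor gives up choosing between results, and the predictor findings become exploratory.

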### **3. Study Design**

This study was designed as a **prospective, randomized, single-center clinical trial**. The study was approved by the local ethics committee (Decision No: 14, Protocol No: 2025/74) and prospectively registered at ClinicalTrials.gov (Identifier: NCT06935500). Participants were enrolled between March 2025 and December 2025 and randomly assigned in a 1:1 ratio using a simple randomization method.

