### **Secondary Outcomes**

- Stone-free rate at 1 month
- Operative time
- Balloon dilation requirement
- Ureteral injury (Traxer classification)
- JJ stent placement

- Postoperative complications (Clavien–Dindo classification)

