## **7. Assessment of Surgeon Stress**

Surgeon stress was assessed using the **State–Trait Anxiety Inventory (STAI-TX1)**. The 20-item state anxiety scale was administered immediately before and after each procedure by an independent investigator. An increase in postoperative STAI-TX1 score compared to preoperative score ( $\Delta\text{STAI-TX1} > 0$ ) was defined as a stress-related procedure.

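### The only regression model for the primary outcome adjusts for operative time, a post-randomisation secondary outcome, so its odds ratio for caliber need not be the effect in the primary objective

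*Combined protocol and SAP*

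**What the plan says.** The primary objective in Section 2 is "To evaluate the impact of ureterorenoscope diameter on intraoperative surgeon stress during ureterorenoscopy". The primary outcome in Section 6 is binary: "Occurrence of stress-related procedures", meaning a rise in STAI-TX1 score from before to after the procedure. Section 7 says that the scale was "administered immediately before and after each procedure by an independent investigator". Under Section 3, patients were "randomly assigned in a 1:1 ratio using a simple randomization method".

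Section 9 states the role of the regression: "Multivariable logistic regression analysis was performed to identify independent predictors of stress-related procedures". It lists four variables: ureteroscope caliber, stone size, stone location and operative time. It then says "Adjusted odds ratios (aOR) with 95% confidence intervals were calculated". Section 6 also lists "Operative time" among the secondary outcomes.

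Separately, Section 9 has a generic bullet that begins "Categorical variables: Chi-square or" and goes on to Fisher's exact test. It is not tied to any particular outcome. No analysis in the document is called primary.

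**The concern.** The same variable is an outcome of the intervention in Section 6 and an adjustment variable for that intervention in Section 9. Operative time accrues after allocation and before the post-procedure stress score, which is where a mediator would sit. In a randomised trial, the impact of diameter on stress reads naturally as the total effect of the allocated scope, including any part that arises because the operation takes longer or shorter.

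Two problems follow if caliber affects operative time:

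- **A different effect.** Holding time fixed removes the part of the caliber effect that runs through time. What remains is at best a direct effect.
- **Loss of the randomised comparison.** Case difficulty that stone size and location do not capture may drive both time and stress. Among operations of equal length, the two groups then differ in difficulty, and the odds ratio can depart from 1 even if caliber has no effect on stress.

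This model is the only place where the plan specifies an effect estimate with a confidence interval. A reader could therefore take its odds ratio for caliber as the trial's answer.

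**Working it through.** **The plan's own figure.** Section 9 gives 65 patients per group (power 95%, alpha 0.05), based on stone-free rates that are not stated. It can be neither reproduced nor refuted from the documents. The point does not depend on it; it serves below only as the trial size, 2 × 65 = 130.

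**Role of each variable.**

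| Variable | When fixed | Other role in the plan |
|---|---|---|
| Caliber | At randomisation | The intervention |
| Stone size, stone location | Before surgery | Stone characteristics (Section 8) |
| Operative time | During surgery, before the second stress score | Secondary outcome (Section 6) |

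Only the last row is a problem.

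**Size under assumed coefficients.** The documents give no coefficients, so every one here is an assumption. Let T = 1 for the standard scope, S be standardised stone size, L a binary location, U unmeasured difficulty, and M operative time with a residual SD of 1:

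- M = a·T + 0.5·S + 0.3·L + g·U + error
- log-odds of stress = −0.3 + d·T + b·M + 0.3·S + 0.3·L + g·U

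With g = 0, the model with operative time targets exp(d). The total effect at fixed error is exp(d + a·b). Averaged over the error, it lies somewhat closer to 1 because odds ratios are non-collapsible. Odds ratios fitted to 400,000 simulated records were:

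| Scenario | a, d, b, g | exp(d + a·b) | Unadjusted | Adjusted for S, L | Also adjusted for time |
|---|---|---|---|---|---|
| Pathways agree | 0.5, 0.5, 0.6, 0 | exp(0.80) = 2.23 | 1.98 | 2.10 | 1.66 |
| Wholly through time | 0.8, 0, 0.8, 0 | exp(0.64) = 1.90 | 1.68 | 1.77 | 1.01 |
| Pathways oppose | −0.5, 0.8, 0.6, 0 | exp(0.50) = 1.65 | 1.53 | 1.60 | 2.25 |
| Caliber does not affect time | 0, 0.7, 0.6, 0 | exp(0.70) = 2.01 | 1.82 | 1.92 | 2.03 |
| No effect on stress, unmeasured difficulty | 0.5, 0, 0, 0.7 | exp(0) = 1.00 | 1.01 | 1.01 | 0.87 |

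In the first four rows the last column matches exp(d) within simulation error: 1.65, 1.00, 2.23 and 2.01. It recovers the direct effect whatever the total effect is. The fourth row's shift, 1.92 to 2.03, is non-collapsibility alone. In the fifth row there is nothing to find, yet adjusting for time produces 0.87.

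**Rejection rates** for the caliber term, from 1,000 simulated trials of 130 patients (Monte Carlo SE at most √(0.25/1000) = 1.6 percentage points), adjusted for S and L, then also for time:

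- Pathways agree: 51% to 27%.
- Wholly through time: 33% to 5%.
- Pathways oppose: 25% to 53%.

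The two models test different effects, so these are not simply gains or losses of power.

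**Dependence on the sign of the caliber–time effect.** A second set of runs fixed the direct log odds ratio at 0.4, so exp(0.4) = 1.49, and the log odds ratio per SD of time at 0.7 to 1.0. Only the standard scope's effect on time was varied:

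| Effect on time | Without time | With time |
|---|---|---|
| +0.5 to +0.8 SD | 1.97–2.74 | about 1.5 |
| +0.2 SD | 1.63–1.64 | 1.49–1.50 |
| 0 | 1.39–1.43 | 1.48 |
| −0.5 SD | 0.91–1.05 | 1.48–1.50 |
| −0.8 SD | 0.71–0.87 | 1.49–1.50 |

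The odds ratio with time stays near 1.5 throughout, while the total effect runs from well above 1 to below 1.

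**The case against.** **An unadjusted comparison is already planned.** The primary outcome is categorical, so the chi-square or Fisher test covers it, and under randomisation that test addresses the total effect. This stands in part. A reader might infer that nothing in the plan addresses the primary objective, and that would be wrong. But the test is not assigned to the primary outcome, nothing ranks it above the regression, and no effect estimate with an interval is specified for it.

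**The model's stated purpose is to find predictors.** Section 9 does not call its odds ratio the primary effect estimate. That is correct, and a predictor model is legitimate exploratory work. Here, however, it contains the randomised factor, uses the primary outcome and is not labelled exploratory.

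**Caliber may not change operative time.** A reader might take it as given that the standard scope prolongs surgery. The documents do not say so: Section 1 treats the influence of diameter on technical outcomes as an open question, and listing time as a secondary outcome means only that it is compared. This stands, and it is why the point is conditional. Still, an analysis of the primary outcome should not rest on one of the trial's own secondary outcomes showing no effect.

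**The distortion usually runs toward no effect.** This too is tempting, but it holds only if the direct and time pathways act in the same direction. The documents do not give the sign of either pathway, and the opposing scenarios show a shift away from the null or a change of sign.

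**Conclusion.** The concern holds in conditional form. The only regression model for the primary outcome conditions on a variable that arises after randomisation and is itself a trial outcome. If caliber affects operative time, the odds ratio for caliber is at best a direct effect, open to bias from unmeasured difficulty, and not the total effect in the primary objective.

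Neither the direction nor the size can be fixed from the documents. Under the assumed coefficients, the change ranges from removing an odds ratio of 1.77 entirely to inflating one of 1.60 to 2.25. If caliber leaves time unchanged, the mediation problem disappears and the shift is small. What does not depend on any assumption is that the plan uses operative time in both roles and does not say which analysis answers the primary objective.

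**What to change.** In Section 9:

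1. Remove operative time from the model used to estimate the caliber effect.
2. Name the comparison by allocated group as the main result for the primary outcome: either a logistic model with caliber, stone size and stone location, or the unadjusted test accompanied by an effect estimate and 95% confidence interval.
3. State when this choice was made. Section 3 describes enrolment as having run from March to December 2025, and Section 9 describes the analyses in the past tense, so the choice should not be presented as prespecified unless a dated record shows that it was.
4. If the time pathway is of interest, report the model with operative time separately as exploratory, and do not present its odds ratio as the effect of caliber.

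The cost is a short change of wording and one re-run of the logistic model. No new data are needed.

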## **8. Data Collection**

Collected variables included:

- Demographics (age, sex, BMI)
- Stone characteristics (size, location, side)
- Operative time
- Perioperative outcomes
- STAI-TX1 scores

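### The primary-outcome analyses leave out the pre-procedure STAI-TX1 score, which is collected and built into the outcome, so chance imbalance goes uncorrected and some power is lost

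*Combined protocol and SAP*

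**What the plan says.** - **Outcome.** Section 6 makes a stress-related procedure the primary outcome. Section 7 defines it: "An increase in postoperative STAI-TX1 score compared to preoperative score", that is, post minus pre above zero.
- **Measurement.** Section 7: "The 20-item state anxiety scale was administered immediately before and after each procedure by an independent investigator". A pre-procedure score should therefore exist for every procedure, and Section 8 lists "STAI-TX1 scores" among the data collected.
- **Model.** Section 9: "Multivariable logistic regression analysis was performed to identify independent predictors of stress-related procedures". Four variables follow: "Ureteroscope caliber", the size of the stone, "Stone location" and operative time. The pre-procedure score is not among them.
- **Other test.** For categorical variables Section 9 names chi-square or Fisher's exact, which take no covariates. It does not say whether this test or the logistic model is the primary comparison of the arms. No analysis adjusted for the pre-procedure score is described anywhere.
- **Design.** Section 3 gives 1:1 simple randomization and mentions no stratification. Section 9 gives 65 per group, derived from stone-free rates and not from the stress outcome.

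**The concern.** Reducing a change score to rise or no rise does not remove its dependence on the starting value. Unless pre and post scores are almost perfectly correlated, a procedure that starts from a low score is more likely to show a rise than one that starts from a high score, whichever scope is used. The plan holds this prognostic value for every procedure and does not use it.

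Two things are at stake. First, simple randomization at this size can leave the arms with different mean pre-procedure scores by chance, and nothing in the design or the analysis corrects the resulting shift in the caliber comparison. Second, the test of caliber has less power than the same data could give. Both apply whichever of the two Section 9 analyses is the primary one, since neither uses the score.

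**Working it through.** **Inputs from the documents.** 65 per arm, 1:1 simple randomization, outcome = post above pre, and the four model variables.

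**The plan's own figure.** The 65 per group (power 95%, alpha 0.05) cannot be reproduced, because the stone-free rates are not given. With a two-sided test and no continuity correction it fits, for example, 95% vs 71.9% or 90% vs 63.8%. It says nothing about power for the stress outcome.

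**Assumed inputs.** The documents give no STAI mean, SD, pre-post correlation r or expected shift. Assumed: normal scores with SD 8, rounded to whole points; a true shift of 0 or 4 points (4/8 = 0.5 SD); r from 0.3 to 0.9; procedures independent. The models compared contain arm only, or arm plus the pre-score.

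**Step 1: size of a chance imbalance.** The standard error of the between-arm difference in mean pre-score is sqrt(2/65) = 0.175 SD, or 8 × 0.175 = 1.40 points. The 95% range is ±1.96 × 0.175 = ±0.34 SD. The chance of an imbalance above 0.25 SD is 2 × [1 − Φ(0.25/0.175)] = 0.154.

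**Step 2: what it does under no true effect** (2,000 simulated trials per row, mean 38, range 20 to 80).

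| r | P(rise) at 1 SD below / above mean pre-score | Change in risk difference per SD of imbalance | Rejection, all trials: without / with pre-score | Rejection, imbalance > 0.25 SD: without / with |
|---|---|---|---|---|
| 0.3 | 0.75 / 0.21 | 0.243 | 0.050 / 0.053 | 0.118 / 0.054 |
| 0.5 | 0.69 / 0.26 | 0.188 | 0.045 / 0.048 | 0.096 / 0.056 |
| 0.7 | 0.63 / 0.31 | 0.154 | 0.043 / 0.044 | 0.088 / 0.042 |
| 0.9 | 0.54 / 0.36 | 0.084 | 0.044 / 0.049 | 0.065 / 0.058 |

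An imbalance at the edge of the 95% range moves the risk difference by 0.34 × 0.243 = 0.08 at r = 0.3 and by 0.34 × 0.084 = 0.03 at r = 0.9. Averaged over all trials, the risk difference was within 0.002 of zero in every row. The last column rests on about 0.15 × 2,000 = 300 trials per row, so its simulation error near 0.05 is about sqrt(0.05 × 0.95/300) = 0.013. The r = 0.9 pair is therefore not distinguishable.

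**Step 3: power for a 4-point shift.** In the same simulation, power without and with the pre-score was 0.474 and 0.571 (r = 0.3), 0.599 and 0.684 (r = 0.5), 0.818 and 0.857 (r = 0.7), and 0.999 in both models (r = 0.9). Four separate runs at r = 0.4, 0.6 and 0.8 gave:

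| r | Power without | Power with | Gain in each run (points) |
|---|---|---|---|
| 0.4 | 52–56% | 62–66% | 8, 10, 10, 10 |
| 0.6 | 70–72% | 76–77% | 4, 5, 5, 6 |
| 0.8 | 93–94% | 94–96% | 1, 1, 2, 2 |

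**Step 4: where the gain comes from.** One of those runs (1,500 trials) also gave the caliber odds ratio (OR) and the standard error (SE) of its logarithm.

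| r | OR without / with | SE of log OR without / with | ln(OR)/SE without / with |
|---|---|---|---|
| 0.4 | 2.11 / 2.55 | 0.364 / 0.416 | 2.05 / 2.25 |
| 0.6 | 2.51 / 2.95 | 0.369 / 0.406 | 2.49 / 2.66 |
| 0.8 | 3.63 / 3.98 | 0.386 / 0.407 | 3.34 / 3.39 |

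The standard error rises with adjustment. Power improves because the odds ratio conditional on the pre-score lies further from 1, and by proportionally more than the standard error grows.

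**The case against.** The strongest reply is that nothing here is invalid. Regression to the mean acts equally on both randomized arms in expectation, and chance imbalance is already covered by the nominal error rate. Step 2 bears this out: overall rejection without the pre-score is 0.043 to 0.050, and it is raised only if one looks solely at the trials with a marked imbalance. This stands. A reader might infer that regression to the mean biases the caliber comparison, or that the chi-square test is defective; the design does not support either inference. Nor can the pre-score be called the strongest determinant of a rise. The documents give no distribution or correlation, and the dependence weakens as r increases.

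It is also fair to say that adjustment does not narrow the interval on the log odds scale (Step 4), and that the adjusted odds ratio answers a different, conditional question. Both stand and belong in the report.

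A third reply concerns timing. The documents do not say whether the surgeon knew the assigned scope when the pre-score was taken. If so, the score is measured after allocation is known, and adjusting for it could remove part of the caliber effect. This limits the fix but does not defend the present plan, because the change score already contains the same pre-score.

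Finally, the score belongs to the surgeon, and the number of surgeons is not stated. If a few surgeons supplied all the scores, the figures above, which treat procedures as independent, need not apply.

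**Conclusion.** The point holds as one of covariate choice and efficiency, not of validity. A collected value that forms part of the primary outcome is used in neither Section 9 analysis. As a result, a chance imbalance at the edge of its 95% range would move the risk difference by about 3 to 8 percentage points uncorrected. Power for a half-SD shift is lower by about 10 percentage points at r = 0.4, about 5 at 0.6 and 1 to 2 at 0.8, with no loss at 0.9. These sizes rest on an assumed SD of 8, a 4-point shift and independent procedures, none of which the documents supply. The omission itself is certain from the text.

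A reader might also take this as an argument for removing operative time from the model. That is a separate matter, and nothing above depends on it.

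**What to change.** 1. Add pre-procedure STAI-TX1 as a continuous covariate to the logistic model for the primary outcome.
2. Report the caliber adjusted odds ratio from that model alongside the unadjusted result. State that the adjusted ratio is conditional on the pre-procedure score and that its log-scale standard error is expected to be larger.
3. State whether the pre-procedure score was taken before the surgeon knew the assigned scope. If it was not, or if this cannot be established, present the adjusted estimate with that caveat.
4. The document is written in the past tense and Section 11 records no amendments, so label the adjusted analysis as added after the plan.

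The cost is small: one covariate from data already listed in Section 8, a few lines of SAP text and a re-run of one model.
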